
refractory pain conditions to widespread societal use for clinical pain.

2. **Objectives** (include all primary and secondary objectives)
 1. **Primary Aim 1: Evaluate the magnitude and duration of combined dronabinol and hydromorphone to reduce pain sensitivity in a validated model of pain.** We hypothesize that the addition of a dronabinol to hydromorphone will result in a dose-dependent increase in the magnitude and duration of analgesia in patients undergoing a validated laboratory model of pain.
 2. **Primary Aim 2: Evaluate the subjective responses to combinations of dronabinol and hydromorphone to determine the subjective, euphoric effects of the combination products.** We hypothesize that dronabinol will not increase the subjective ratings of positive drug effects or other proxy measures of abuse liability, relative to hydromorphone alone.
 3. **Primary Aim 3: Evaluate the degree to which combining dronabinol with hydromorphone impacts neurocognitive performance.** We hypothesize that dronabinol may reduce neurocognitive performance at high doses, relative to hydromorphone alone, though the degree to which this may occur is unknown. This aim is critical for the advancement of potential opioid/cannabinoid combination products.
 4. **Secondary Aim 1: Evaluate whether there are sex differences on study outcomes.** We hypothesize that dronabinol enhancement of hydromorphone-analgesia will be greater among female vs. male subjects.
3. **Background** (briefly describe pre-clinical and clinical data, current experience with procedures, drug or device, and any other relevant information to justify the research).

This study will systematically evaluate whether cannabinoids can enhance the analgesic efficacy of opioids, which will advance the use of cannabinoids for the treatment of acute and/or chronic pain.

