
Conclusion: This will be the 1st human laboratory study to evaluate combinations of cannabinoids and opioids on a comprehensive and validated quantitative sensory testing battery, and the results of this study will identify whether a signal for this medication combination exists that should be advanced into randomized controlled trial evaluations with clinical pain populations. This study will also assess aspects that would impact drug development (abuse liability, neurocognitive impairment) and the effect of participant sex on outcomes. The ultimate goal of this research will be to determine which medication/dose combinations may exert strong analgesic effects, while minimizing abuse liability and cognitive deficits, in order to advance these medications into clinical trials for the treatment of chronic pain. This is a logical first step towards evaluating combined cannabinoid/opioids treatments for chronic pain, and will provide data necessary to support numerous evaluations of combination treatments for this population.

4. Study Procedures

- a. Study design, including the sequence and timing of study procedures (distinguish research procedures from those that are part of routine care).

Project Overview: This study will enroll 100 healthy adults, and will aim to complete 60 (30 men, 30 women) participants. Participants will conduct a within-subject evaluation of the degree to which the FDA-approved cannabinoid dronabinol (Marinol) enhances the analgesic effect of the prototypic opioid hydromorphone (Dilaudid). Subjects will complete a Screening visit to establish study eligibility and 5 experimental sessions. Experimental sessions will occur approximately once weekly and will permit subjects to admit themselves into the clinical research unit the night before the session if interested. Subjects will be provided with taxi service to and from the session. Subjects will receive a dose of hydromorphone (4mg, oral) and a double-blind oral dose of study drug or placebo the

morning of each experimental session, and will undergo QST measures of laboratory evoked pain, provide self-report ratings of drug effects, and complete a neurocognitive battery. The order of sessions will be randomized with the exception of Session 1, which will always be active hydromorphone + placebo to ensure the participant has a safe response to hydromorphone before proceeding into the remaining sessions.

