The morning of each experimental session, the subject will receive a calorie-controlled breakfast each morning. Following breakfast, subjects will complete a baseline rating of QST and self-report measures (from which all subsequent ratings will be compared for data analysis purposes). An oral capsule containing either study drug or placebo will then be administered and hydromorphone (4mg oral in four sessions and a placebo oral dose in one session) will be administered. The time of drug administration will be selected to enable both dronabinol and hydromorphone to exert peak effects at the same time. Subjects will complete QST (see below) and self-report measures at regular intervals following study drug administration. Self-report measures will include specific opioid agonist and antagonist effects, to assess whether cannabinoids are exerting an effect on a particular category of opioid agonist symptom, and will capture whether any negative effects (e.g., nausea) occur as a function of the cannabinoid dose. Frequent collection will enable evaluation of time to peak drug effects, duration of effects, and general time course of effects and is a widely used and accepted approach in laboratory studies of drug effects. During the final assessment each day, subjects will complete a Drug vs. Money Questionnaire to indicate the dollar value they would place upon the drugs received⁹⁸. This is a well-accepted proxy measure of abuse liability. Study staff will document adverse events throughout the study and any subject who experiences a strongly unpleasant effect of the medications will be able to end participation. Any subject who is experiencing strong agonist effects at the end of the session will be provided overnight accommodation in the CRU; based on our experience we expect this to be minimal and are budgeting for 10% of sessions to have a 2nd night.

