Quantitative Sensory Testing (QST) Measures of Laboratory Evoked Pain: Subjects will complete a state-of-the-art quantitative sensory testing (QST) battery, which will comprehensively and systematically measure pain sensitivity. This approach will provide information regarding the full range of analgesic effects possible, across a wide variety of psycho-physiologically-mediated, experimentally-induced measures of pain perception. Subjects will complete a baseline QST session prior to study drug administration on each experimental session day, and will complete the pain testing battery at regular intervals during the experimental session day. Each administration of the QST battery will take 20-30 minutes. The QST battery will consist of threshold and tolerance, temporal summation, and conditioned

pain modulation (CPM) tests. The threshold responses will be conducted in randomized and counter-balanced order, and conditioned pain modulation will always occur last.

Threshold Responses will be assessed using thermal and pressure stimulation. *Thermal threshold:* All contact heat stimuli will be delivered using a peltier-element-based stimulator (Medoc, Israel). Two trials of heat pain threshold will be administered using an ascending method of limits paradigm. The thermode will gradually increase in temperature (rate of rise = .5°C/sec) from a pre-set baseline (31°C), until the subject indicates when the stimulus “first feels painful” (threshold, HPT_h) and presses a button (which terminates the procedure) indicating that the pain is intolerable (tolerance, HPT_o). *Pressure threshold:* A pressure algometer will be utilized to assess responses to pressure stimulation at a variety of anatomical sites in a randomly determined order. The pressure algometer (Somedic; Sweden) uses a rubber probe covered with 1mm polypropylene material; pressure at the site is gradually increased at a steady rate. Subjects indicate when the stimulus is first perceived as painful, which terminates the application. The algometer produces a sensation of localized pressure; technicians will place the probe of the algometer in the center of each muscle group or anatomic site when delivering the mechanical stimuli. Thirty-second inter-stimulus intervals will be maintained for all stimuli. Each trial will be averaged together to result in one HPT_h, HPT_o, and PPT_h measure.

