Hydromorphone (Dialudid) is a potent mu-opioid agonist that we have extensive experience administering in controlled laboratory settings. Hydromorphone is not subject to differences in CYP metabolic enzymes (in contrast to other opioids such as oxycodone) and therefore will not require us to screen out individuals with recent exposure to CYP inhibitors/inducers, or to analyze/statistically control for CYP metabolic profiles. We have selected a 4mg oral hydromorphone dose for this study because we have data from another ongoing study (IRB00047423) indicating it produces a mild-moderate effect (versus a ceiling or floor effect) and will therefore allow us to visualize changes as a function of the dronabinol. 4mg oral hydromorphone is also a dose that is commercially available and regularly prescribed for analgesia, which increases the clinical relevance of this study. Based on clinical experience, we expect it to produce a moderate analgesic effect on pain. This is an important feature because too strong a dose could overwhelm the cannabinoid effect and prevent us from effectively evaluating the study hypotheses. A moderate dose of hydromorphone will better enable us to evaluate shifts in the analgesic curve as a function of the study drug, and provide a stronger assessment of whether cannabinoids will enhance the analgesic effect of hydromorphone.

Study Drug Dosing		
Condition	Hydromorphone Oral	Dronabinol Oral
Nonrandomized 1	4mg	Placebo
Randomized 2	4mg	2.5mg
3	4mg	5mg
4	4mg	10mg
5	placebo	placebo
Session 1 will be nonrandomized and used as a safety screening day. Sessions 2-5 will be randomized and counter-balanced across participants.		

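### Hydromorphone alone is scheduled once, always in the non-randomised Session 1, so dronabinol-versus-hydromorphone-alone contrasts are aliased with the first session and the Aim 3 session covariate cannot undo this

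*Combined protocol and SAP*

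**What the plan says.** **Schedule.** Section 4.a (Project Overview): "The order of sessions will be randomized with the exception of Session 1, which will always be active hydromorphone + placebo". The reason given is safety. The note to the dosing table in section 6.a repeats it: "Session 1 will be nonrandomized and used as a safety screening day". That table places only the three combinations (hydromorphone 4 mg with dronabinol 2.5, 5 or 10 mg) and placebo/placebo in the randomised Sessions 2-5. Section 4.a counts four active hydromorphone sessions. Three of them carry dronabinol, so one is hydromorphone alone.

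**Hypotheses (section 2).**
- Aim 1: "the addition of a dronabinol to hydromorphone will result in a dose-dependent increase in the magnitude and duration of analgesia".
- Aim 2: "dronabinol will not increase the subjective ratings of positive drug effects or other proxy measures of abuse liability, relative to hydromorphone alone".
- Aim 3: "dronabinol may reduce neurocognitive performance at high doses, relative to hydromorphone alone".

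**Analysis (section 7.a).** Aim 1 uses a drug condition by time mixed model with Tukey post-hoc tests. Aim 2 uses a repeated measures ANOVA by dose on Drug vs. Money. Neither names a session term. Aim 3 adds session number as a covariate, numbered 1 to 6, to deal with practice effects. It does not say whether the covariate is linear or categorical.

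**Baselines (section 4.a).** "Subjects will complete a baseline QST session prior to study drug administration on each experimental session day". Pre-dose QST and self-report values are those "from which all subsequent ratings will be compared for data analysis purposes". No pre-dose cognitive test is described. For the Aim 2 outcome: "During the final assessment each day, subjects will complete a Drug vs. Money Questionnaire". Section 7.a makes change from baseline conditional on large baseline variation in general, but compares CPM and cold-water tolerance with baseline without that condition. Section 7.c sizes the trial on peak change from baseline.

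**The concern.** A within-subject comparison protects against session effects only if the conditions being compared are balanced over sessions. Here one of them never moves. Anything particular to a first visit, such as novelty of the pain battery, an unpractised cognitive test or a first exposure to the opioid, enters the hydromorphone-alone mean and no dronabinol mean.

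The stake is the comparison that Aims 2 and 3 are worded around, and the part of Aim 1 about adding dronabinol. A first-session effect could create or hide enhanced analgesia, or create or hide an increase in drug value. In Aim 3 it could mask or imitate impairment. A larger sample does not help, because it makes a biased contrast significant more often. Section 3 says the results will show whether a signal exists to advance into clinical trials, so a non-randomised contrast should not be read as a randomised one.

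**Working it through.** The plan gives no figure for session effects. Its one related figure, power 0.95 in section 7.c, is not in dispute. With 6 conditions, f = 0.2, N = 45 and assumed correlation 0.5, lambda = 0.04 × 45 × 6 / 0.5 = 21.6, which gives power 0.96. It does not depend on session order.

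**1. Estimability.** Design matrix over all 24 orders of Sessions 2-5, one subject per order, with subject and condition effects:

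| Model | Columns | Rank |
|---|---|---|
| Condition only | 28 | 28 |
| + linear session | 29 | 29 |
| + Session 1 indicator | 29 | 28 |
| + categorical session | 32 | 31 |
| Sessions 2-5 only, categorical session | 30 | 30 |

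Once session is free to vary, dronabinol minus hydromorphone alone cannot be estimated. Contrasts within Sessions 2-5 can.

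**2. What a linear covariate does.** Let f(s) be the practice gain by session, with f(1) = 0 and f(5) = 1. Each dronabinol dose is spread evenly over Sessions 2-5, whose mean position is 3.5. The slope b is learned from Sessions 2-5 only and extrapolated 2.5 sessions back:

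- bias without covariate = mean of f(2) to f(5)
- bias with covariate = that mean − 2.5b, where b = Σ(s − 3.5)f(s)/5

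Example, halving curve: f = 0.533, 0.800, 0.933, 1.000. The mean is 0.817 and b = 0.767/5 = 0.153, so the bias is 0.817 − 0.383 = 0.43.

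| Assumed curve | Without covariate | With linear covariate |
|---|---|---|
| Linear | 63% | 0% |
| Logarithmic | 74% | 27% |
| Halving | 82% | 43% |
| First-session step | 100% | 100% |
| Convex (session squared) | 52% | −21% |
| Gain between Sessions 3 and 4 | 50% | −50% |

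Figures are shares of the Session 1-to-5 gain. Positive bias flatters dronabinol sessions and hides impairment; negative bias suggests impairment. The price in precision: the contrast variance goes from 2σ²/n to (2 + 2.5²/5)σ²/n = 3.25σ²/n. The ratio is 1.625, so the SE rises by 27.5%.

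**3. Sensitivity of the Tukey tests.** Assumptions: no drug effect, five conditions, total variance 1, residual variance 1 − correlation, df 4(n − 1), 100,000 simulated trials per cell. Shifts are in SD of the analysed outcome, after any baseline correction. Sections 7.c and 4.a give 50 and 60 completers. Correlation 0.5 represents raw scores. Correlation 0 represents change from one pre-dose to one post-dose value with no stable individual drug response, where subject and session terms cancel.

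| Session 1 shift (SD) | n=50, corr. 0.5 | n=50, corr. 0 | n=60, corr. 0.5 | n=60, corr. 0 |
|---|---|---|---|---|
| 0 | 2% | 2% | 2% | 2% |
| 0.1 | 6% | 4% | 6% | 4% |
| 0.2 | 20% | 10% | 25% | 12% |
| 0.3 | 48% | 23% | 57% | 29% |
| 0.4 | 78% | 43% | 86% | 52% |

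Entries are the chance of at least one false dronabinol-versus-hydromorphone-alone result.

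**4. Tipping point.** The Tukey critical difference at n=50 is 0.389 SD at correlation 0.5 and 0.551 SD at correlation 0. At 0.5, an observed 0.5 SD difference loses significance if 0.5 − 0.389 = 0.11 SD of it is a Session 1 shift. At correlation 0 that difference is not significant to begin with, so the 0.11 SD figure does not apply.

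**5. Can the baselines clear the contrast?** For QST and self-report, Session 1 pre-dose values can be compared with those of Sessions 2-5. SE = √(1.25 × 0.5/50) = 0.112 SD, so the 95% half-width is 0.22 SD (correlation 0.5, n=50). That exceeds 0.11 SD, so a non-significant check does not clear a raw-score contrast. Nor can it detect a Session 1 difference in post-dose response.

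**The case against.** The strongest defence is that the order is disclosed, has a safety reason, and belongs to a signal-finding study whose first hypothesis is about dose dependence. All of that stands. Dose-to-dose and placebo/placebo contrasts lie within randomised Sessions 2-5, so the dose-dependence part of Aim 1 remains partly testable. A reader might infer that none of the trial's comparisons is randomised; the schedule does not support that.

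Second, every session has a pre-dose QST and self-report baseline, and cold-water tolerance is already compared with baseline unconditionally. (For CPM, the baseline might mean the value before hand immersion.) This also stands, but it removes only a shift in level.

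Third, shift sizes are assumed, and the rates at correlation 0.5 overstate the risk for change scores without stable individual drug response. Both correlations are therefore shown.

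Two more readings go too far. One is that Aim 3 must be biased towards missing impairment: that holds if practice decelerates, which is plausible but assumed, and convex or late gains reverse it. The other is that the missing pre-dose Drug vs. Money value is a flaw: the questionnaire values drugs already received, so none can exist. It limits correction and is not a defect.

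The wash-out addresses tolerance and carry-over, and progesterone addresses hormone status. Neither separates Session 1 from its treatment.

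**Conclusion.** The concern holds for the five-session schedule in sections 4.a, 4.b and 6.a. Every dronabinol-versus-hydromorphone-alone contrast is aliased with Session 1. The Aim 1 and Aim 2 models ignore this, and the Aim 3 covariate cannot control practice effects for this contrast in either form.

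The aliasing follows from the schedule alone. Its consequences rest on assumed shifts: at n=50, 0.1 to 0.4 SD gives false-positive rates of 6% to 78% at correlation 0.5, or 4% to 43% at correlation 0. These show sensitivity. They are not estimates of likely error, and the documents do not show that any Session 1 effect exists or which way it runs.

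One fact could soften the point. Sections 5 and 8.b still mention a Qualifying session involving hydromorphone, which the five-session schedule does not contain. If it takes place, Session 1 is not the first exposure and novelty is smaller, but the fixed order remains. The point should be settled before the analysis is fixed, because it bears on what each primary aim can conclude.

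**What to change.** Leave Session 1 where it is, and change the analysis and labelling.

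1. Analyse randomised Sessions 2-5 in their own model with session as a categorical effect. Report dose-to-dose contrasts and the 2.5-10 mg trend as the randomised evidence, and state that these do not by themselves answer Aims 2 and 3.
2. Report the hydromorphone-alone contrasts from a separate model, labelled non-randomised, each with the Session 1 shift that would overturn it.
3. Remove the statement that the Aim 3 covariate controls practice effects for these contrasts.
4. Use each session's own pre-dose value for QST and self-report, as a covariate or as change from baseline, with one rule fixed per outcome in advance. Report the Session 1 minus Sessions 2-5 baseline difference with its confidence interval.
5. Reconcile the five sessions with the session numbering to 6 in section 7.a, the six conditions in section 7.c and the Qualifying session in sections 5 and 8.b.

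The cost is SAP wording, one extra model and one table, with no extra visits. The hydromorphone-alone conclusions become weaker, and no analysis can make them randomised. The trend may have little power: at n=50 and correlation 0.5 it is 0.57 if the effect is linear in dose up to 0.4 SD, 0.17 for effects of 0.25/0.35/0.40 SD, and 0.05 if it plateaus at 0.4 SD from the lowest dose. Change scores can also cost precision, which is why item 4 leaves the choice open. A randomised repeat of hydromorphone alone would break the aliasing, but it alters drug exposure and visits and is not proposed here.

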Temporal Summation (TS) of Pain will be assessed in 2 ways, using repetitive thermal stimuli and repetitive punctate stimuli. Sequences of 10 heat pulses will be applied using the Medoc. (Note: within each 10-pulse sequence, the temperature of each phasic stimulus is the same). Within each sequence, successive thermal pulses at a given temperature will be delivered for a duration of approximately 0.5 sec each, with an approximately 2.5-sec inter-pulse interval. Subjects will verbally rate the perceived intensity of each thermal pulse on a 0-100 rating scale and may terminate the procedure at any time. Windup is measured as the differences between the highest rated thermal stimulus and the 1st thermal stimulus.⁹⁹

Mechanical Temporal Summation will be studied using punctate stimulators (a set of weighted pinprick stimulators with fixed stimulus intensities (flat contact area of 0.2 mm diameter) that exert forces of 8- 512 mN). The probes are applied perpendicular to the skin. We will apply both single stimuli and 10-stimulus trains at 1HZ, and will record the subjects pain rating (0-100). Single pinprick stimuli are alternated with the trains of 10 stimuli. The mean pain rating of 10-stimulus trains divided by the mean pain rating to single stimuli is then calculated as a ratio.¹⁰⁰

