Cold Pressor Testing and CPM: A series of procedures designed to elicit and measure endogenous inhibition of pain will be applied. In the present protocol, subjects will undergo a series of cold pressor tasks (i.e., the conditioning stimuli) consisting of immersion of the hand for up to 1 minute in a circulating cold water bath. During hand immersion, pressure responses or temporal summation will be re-assessed while subjects’ hands remain in the cold water. Subjects may remove their hand at any time. Two minutes after finishing the first immersion, subjects will re-immerses their hand in the water, and one of these tests will be re-assessed, each separated by 2 min and identical to the first 2 trials (the tests will be conducted in random order). CPM Index is quantified as the average percent change (across trials) in PPT_h or TS during the cold pressor tasks relative to baseline ratings [(PPT_h or TS during cold pressor/PPT_h or TS prior to cold pressor)*100].¹⁰¹ One final cold-water immersion will be performed at the conclusion of the CPM procedures. This will involve a typical cold pressor task, using immersion of the hand until the subject’s tolerance is reached, with a 5-minute uninformed time limit.

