- **Primary Aim 1:** The primary outcome will be the area under the curve of each QST procedure, which will provide an assessment of the mean duration and magnitude of the drug effect. Primary outcomes will be tested with repeated two-factor (Drug Condition x Time) models to examine main and interaction effects for all raw data as designed. If there is large variation across subjects at the baseline timepoint, the raw data will be transformed as a change from baseline and analyzed in drug condition by time models. Statistical analyses will be conducted using multilevel analyses with an autoregressive covariance structure using SAS PROC MIXED Software¹³¹. These analyses will permit an examination for effects of drug condition and time effects associated within the course of the study. Interpretation of drug condition main effects and interactions will rely on Tukey post-hoc tests. This aim will also assess frequency of adverse events as a function of study drug.

Specific outcome variables for the QST procedures will be as follows:

- a. Heat Pain Threshold and Tolerance: HPT_h and HPT_o in °C (both in normal and capsaicin treated skin)
 - b. Pressure Pain Threshold: PPT_h in kilopascals
 - c. Thermal and Mechanical Temporal Summation: Verbal pain ratings (both in normal and capsaicin treated skin for MTS)
 - d. Conditioned Pain Modulation: The index score of CPM:PPT_h and CPM:TS (compared to baseline) for each dose
 - e. Cold Water Tolerance: Time to tolerance (compared to baseline) for each dose.
- **Primary Aim 2:** The Drug vs. Money questionnaire will be compared across dose conditions, using peak monetary rating for each dose as the primary outcome. Within-subject changes, as a function of dose, will be analyzed using a repeated measures analysis of variance (ANOVA).
 - **Primary Aim 3:** Neurocognitive tests will be compared as a function of study drug dose, using study session number (1-6) as a covariate to control for practice effects. Specific outcome measures will include:
 - a. Divided Attention Task (DAT): Accuracy with which they perform the two tasks
 - b. Digit Symbol Substitution Task (DSST): Accuracy, total number of patterns completed in allotted time
 - c. Computerized version of the Paced Auditory Serial Addition Task (PASAT): Summed of correct trials

b. Secondary outcome variables.

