
Participants will also not be informed about the specific medication they are receiving, which is a common procedure used by our research unit to minimize bias in responding. This procedure also makes it difficult for the

participant to seek out drugs they may have found reinforcing during the study session, thus further minimizing the opportunity for study participation to increase risk of non-study drug abuse.

d. Protection Against Risks of Discomfort from Pain Testing: It is likely that participants will experience some acute and transient discomfort from the pain testing session, however we will work to mitigate that risk as much as possible. First, participants will be informed of the pain testing procedure during the informed consent and will be able to make an informed decision regarding their study participation. Second, we chose standardized pain tests that are known to produce short-lived effects and thus are unlikely to produce any residual pain. Third, the measures rely on the participant ending the pain testing procedure as an outcome measure, which means that all participants are encouraged to remove themselves from the painful stimulus at any time and that they are in control of the magnitude and duration of pain they experience. Fourth, we will enforce an upper limit on both pain measures to prevent any tissue damage from occurring (e.g., hand cannot be in cold presser task for >150 seconds). Fifth, participants will be informed that they can revoke their consent to participate in the pain testing at any time without penalty. Finally, the participants will be monitored 24 hours by study staff and will have access to medical care and concomitant medications to treat residual pain if necessary. We will also document and review all adverse events reported from the pain testing session and will follow any recommendations they may have regarding the cessation of pain testing.

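### Thermal windup has no scoring rule for pulse trains stopped early and cold tolerance no rule for times at the limit, so both drug effects can be understated

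*Combined protocol and SAP*

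**What the plan says.** **Thermal windup.** Section 4.a, Temporal Summation (TS) of Pain: "Sequences of 10 heat pulses will be applied using the Medoc". Participants rate each pulse from 0 to 100 "and may terminate the procedure at any time". The score follows: "Windup is measured as the differences between the highest rated thermal stimulus and the 1st thermal stimulus". Nothing says how to score a train with fewer than 10 pulses. Section 8.b, item d (discomfort from pain testing), adds that "all participants are encouraged to remove themselves from the painful stimulus at any time".

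**Outcome list.** Section 7.a, Primary Aim 1, names this outcome as "Thermal and Mechanical Temporal Summation: Verbal pain ratings" and does not mention the highest-minus-first difference.

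**Cold tolerance.** Section 4.a, Cold Pressor Testing and CPM, ends with an immersion to tolerance "with a 5-minute uninformed time limit". Section 8.b, item d, gives 150 seconds as the longest immersion. Section 7.a lists "Cold Water Tolerance: Time to tolerance", compared with baseline.

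**Analysis.** Section 7.a summarises each QST procedure by its area under the curve and tests drug condition by time in linear mixed models (SAS PROC MIXED). It names no censored-data or time-to-event method and no rule for a value at the limit.

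**The concern.** The two outcomes lose information at opposite ends.

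For windup, stopping early leaves the first rating as it is and removes the later, higher ones. A participant who finds the train intolerable can therefore score as having little pain facilitation. If stopping is driven by pain, it should be commonest under double placebo, then under hydromorphone alone, and rarest under effective combinations. The loss then differs between the conditions being compared. It lowers the comparator's score and so reduces the apparent benefit. A change-from-baseline analysis does not remove this, because the imbalance arises after dosing. More participants do not remove it either. If TS in the CPM:TS index means windup, the same problem enters both parts of that ratio.

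For cold tolerance, removing the hand is the outcome, so nothing is lost by stopping. The loss is at the limit and falls mostly in the most analgesic conditions. A participant at the limit before dosing cannot show a gain.

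Both are Aim 1 primary outcomes.

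**Working it through.** The plan gives no stopping rate, capping rate or windup variance, so there is no stated figure to reproduce. All numerical inputs below are assumptions. Only the scoring rule, the train length and the two limits come from the documents.

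**1. Windup by hand.** Windup = highest rating received − first rating. Suppose comparator ratings start at 40 and rise 5 per pulse (last rating 85), and drug ratings start at 30 and rise 4 (last rating 66).

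| Participant stops on reaching | Comparator | Drug | Measured benefit |
|---|---|---|---|
| never | 85 − 40 = 45 | 66 − 30 = 36 | 9 |
| 80 | 80 − 40 = 40 | 36 | 4 |
| 70 | 70 − 40 = 30 | 36 | −6 |

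**2. Windup by simulation.** Assumed: first rating mean 40, SD 15; rise per pulse mean 4, SD 2; noise SD 3; ratings held to 0–100. The participant stops on reaching a personal limit with SD 10.

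*Drug lowers first rating and rise by 15%; true benefit 3.7 points.*

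| Mean personal limit | Comparator trains stopped | Measured benefit | Share lost |
|---|---|---|---|
| 100 | 10% | 3.3 | (3.7 − 3.3)/3.7 = 11% |
| 90 | 22% | 2.5 | (3.7 − 2.5)/3.7 = 32% |
| 80 | 38% | 1.0 | (3.7 − 1.0)/3.7 = 73% |
| 70 | 54% | −0.8 | reversed |

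Linear interpolation puts zero at about 38 + 16 × 1.0/1.8 = 47% stopped.

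*Drug lowers first rating by 10 points and rise by 20%; true benefit about 5.3 points.*

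| Stopped, comparator vs drug | Measured benefit |
|---|---|
| 2.5% vs 0.5% | 5.3 |
| 16% vs 4% | 4.6 |
| 30% vs 10% | 3.1 |
| 46% vs 20% | 0.8 |
| 63% vs 35% | −1.7 |

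*Drug lowers only the rise, by 20%.* The benefit falls from about 5.8 to 1.4 over the range tried and never reverses. Reversal here needed a drug that also lowers the starting rating, which leaves more room to climb before the limit.

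**3. Cold tolerance.** With limit c, the mean gain is ∫₀ᶜ [S₁(t) − S₀(t)] dt, where S₁ and S₀ are the proportions still immersed at time t with drug and comparator. If the drug only lengthens tolerance, S₁ ≥ S₀ throughout. The capped gain is then never negative and never exceeds the uncapped one.

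Assumed: lognormal times, median 60 s, true ratio 1.30, within-person log-SD 0.3. Each cell gives results for between-person log-SD 0.8 / 1.0.

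| | No limit | 300 s | 150 s |
|---|---|---|---|
| At limit, comparator | 0 | 3% / 6% | 14% / 19% |
| At limit, drug | 0 | 6% / 10% | 22% / 27% |
| Mean gain, s | 26.1 / 31.5 | 21.0 / 20.0 | 13.6 / 11.9 |
| Ratio estimated on log scale | 1.30 / 1.30 | 1.29 / 1.27 | 1.24 / 1.23 |
| Standardised paired effect, raw seconds | 0.40 / 0.32 | 0.49 / 0.47 | 0.51 / 0.48 |
| Standardised paired effect, log time | 0.62 / 0.62 | 0.61 / 0.59 | 0.56 / 0.54 |

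The median matters. At log-SD 0.8, a 30 s median gives gains of 12.9, 12.3 and 10.5 s (no limit, 300 s, 150 s). A 150 s median gives 64.8, 27.4 and 10.3 s.

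**The case against.** **Stopping may be rare.** A train lasts about 10 × 0.5 + 9 × 2.5 = 27.5 s, and Section 8.a expects only mild discomfort from pain testing. With milder assumed inputs (first rating 25, rise 2 per pulse, limit 95), 1% of trains stop and the measured benefit is 2.51 against a true 2.55. This stands: the bias is conditional on a rate that nobody has stated. A reader might infer that windup will come out with the wrong sign. The documents do not support that, since reversal needed about half of comparator trains stopped and a lower starting rating on drug.

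**Windup may not be the analysed score.** Section 7.a lists verbal ratings, and the windup rule carries a citation that may deal with incomplete trains. This stands as a reason to name the score. It does not remove the problem, because raw ratings from stopped trains also lack the later, higher values.

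**The plan does not say that capped times are exact.** Correct. This is inferred from a linear mixed model with no censoring rule.

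**Capping need not cost power.** Also correct for raw seconds: the limit trims the long upper tail, and the standardised effect rises. On the log scale it falls modestly. The understated size of the gain remains, and log time was the more sensitive scale in every column above.

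**Conclusion.** The point holds in conditional form. Followed as written, the windup rule understates a drug benefit whenever pain-driven stopping is commoner in the comparator. Under the stated assumptions the loss is about a tenth at 10% of comparator trains stopped, about a third at 22%, and near zero at 1 to 3%.

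The default handling of cold times at the limit understates the gain. At an assumed 60 s median, a true 1.30-fold gain is estimated as 1.27 to 1.29 with a 300 s limit and 1.23 to 1.24 with 150 s. A reader might infer that the limit could reverse the cold result, or that its losses also fall in the least analgesic condition. Neither follows: the sign is preserved if the drug only lengthens tolerance, and the capped values lie mostly in the more analgesic conditions.

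The 5-minute and 150-second limits contradict each other. Until they are reconciled the censoring time is undefined.

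Nothing here shows the stated sample size or power to be wrong. The change should be made, because it is cheap and because stopping that is not recorded may be impossible to correct for later.

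**What to change.** **Windup.** Leave free stopping as it is. Record the pulse number at which each train ends and report the share of stopped trains by condition. State in Section 7.a which temporal summation score is analysed, including within CPM:TS. Keep windup as the construct, and treat the maximum of a stopped train as right-censored at termination.

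Give two sensitivity analyses, each with its limits stated:
- Completed trains only. This drops the most painful trains.
- Mean rating over 10 pulses, with the last rating carried forward. In simulation with a true difference of 13.2 points it kept 12.8 at 22% stopping and 11.0 at 54%. It measures overall pain, though: with build-up unchanged by drug and 39% of comparator trains stopped, it still showed a 5.9-point benefit. It should not replace windup.

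Carrying the last rating forward into highest minus first changes essentially nothing, so that is not a remedy.

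**Cold tolerance.** Treat times at the limit as right-censored, using a censored mixed model for log time or a Cox model stratified by participant. Report the share at the limit by condition and before dosing. Reconcile the two limits and use the reconciled value as the censoring time.

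**Cost.** One extra field on the QST form, protocol and SAP wording, and slightly more analysis work; no added testing. The price is an assumption for stopped trains: that the level at which a participant stops carries no further information about the build-up that would have followed.
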